The study includes one international site, GIMEMA Foundation, located in Italy. Although [name] has an adjunct appointment at Northwestern University, for the purpose of this study, he will be serving as the site PI at GIMEMA (his primary affiliation), not in his capacity as adjunct faculty at NU.

The GIMEMA site will be obtaining IRB approval externally at their site. Upon approval from GIMEMA's IRB, the approval letter will be uploaded to this submission as a separate modification.

[name] has a strong track record in conducting patient-reported outcome data in Italy. We do not anticipate any cultural or literacy barriers to eligible participants at the GIMEMA site.

All study procedures will comply with the European Union General Data Protection Regulations.

9.0 Procedures Involved:

Aim 1. To develop an online platform for systematic monitoring of patient-reported AE assessment that is tailored to the unique demands of TKI therapy for CML.

We propose to assemble a network of treatment sites across the US (Northwestern University and Augusta University) and Italy (Italian Group for Adult Hematologic Disease, “GIMEMA”), with the goal of developing and piloting a tailored monitoring intervention targeting side effects (i.e., patient-reported AEs) in CML patients undergoing first-line TKI therapy. The tailored monitoring intervention will draw primarily from the well-established PRO-CTCAE Item Library¹⁹, with additional CML-specific items drawn from the FACIT²⁰ and EORTC item²¹ libraries as necessary. While we expect that the majority of selected symptoms will be drawn from the PRO-CTCAE Item Library, we anticipate this might not include specific TKI side-effects. Therefore, a comprehensive list of items for CML patients has to be also drawn from other available sources (FACIT and EORTC). Items to be implemented will be selected based on two criteria: 1) a side effect observed (any grade) in >10% of patients based on clinical trial reports of monotherapy administration; and 2) available in approved and certified English, and Italian versions. At this stage, the main goal will be that of identifying a parsimonious set of items so as to reduce patient burden as much as possible. We will aim for a list not including more than 20 items so as to make this assessment feasible in a busy clinical practice. After having identified this set of relevant AEs items to be monitored (i.e., PRO-CML Survey), we will load the patient assessment and report program into tablets for electronic administration in the clinic setting. CHES enables this administration with an already existing web-based software. Therefore, a common web-based platform, housed at NU, will be used by all participating sites in order to ensure standardization of PRO assessment and outcomes interpretation. At each site, a clinical research staff (CRS) member will be appointed to undergo a standardized 20/30 minute, web-enabled teleconference before initiation of enrollment to learn how to use the secure online platform system. Treating physicians also will be trained to use the web-based platform and interpret graphical display of outcomes. Participating sites will be assessed for wireless internet connectivity in clinic waiting areas and also wireless tablet computers will be provided to sites if needed. Aim 1 does not involve any participant procedures.

Aim 2. To assess patient and physician acceptability and satisfaction with use of this platform in CML routine practice and evaluate its value in improving symptom management, HRQoL, adherence to therapy as well as preliminary efficacy.

If a patient is eligible and would like to participate, the consent procedures will be conducted and patients will be asked in the waiting room (just before the scheduled clinical visit), to complete the newly developed touch-screen PRO-CML Survey. Reasons for refusal to participate will be systematically tracked. At the time of enrollment, the local clinical research staff member will register the participant in CHES platform, which will generate a login ID and password enabling the participant to log in to CHES. The clinical research staff member will instruct each patient to complete self- reported questions via tablet computers. The appointed clinical research staff member will provide technical assistance to patients, if necessary, but will not be allowed to provide assistance in symptom rating. At each clinical visit, a tablet computer will be brought to participants, possibly in a private area of clinic waiting rooms to complete the survey. The clinical research staff member will bring the participant's CHES log-in information up on the tablet, enabling the participant to log in and complete the survey. PRO—CML Survey results will be feed-backed in real time to physicians who will have this data available (in a graphical format to ease interpretation) at the time of consultation on their computers. (No results related to adherence will be communicated to physicians). Similarly, to previous studies²², symptoms will be graded on a five-point scale from 0 (not present) to 4 (severe). At subsequent clinic visits, patients will be reminded by a staff member of the opportunity to log in the system, but such logins will not be mandatory. Similarly, to previous studies²² whether to and how to incorporate a discussion of PRO-CML Survey results into routine visits will be left to patient and their treating physician discretion. In addition, patients will be given a remote access option, enabling completion of the Survey at their convenience, between scheduled clinic visits at home. A clinical research staff member will provide participants with an envelope containing a piece of paper that includes the link to the study on CHES, as well as their log-in information. For home log-in session between visits, there will be no automatic reminders to patients. However, the web-system will be programmed to trigger e-mail alerts to a designated member of the clinical staff, whenever a patient-reported symptom will worsen by >1 point; or will reach an absolute grade of 3. A report tracking participants' PRO-CML Survey symptoms will be printed at each clinic visit for the treating physician. No specific guidance will be provided to physicians about what actions to take in response to alerts or printed symptom profiles²². We intend to provide this intervention for the first six months of treatment, typically covering 8-10 clinical encounters. We anticipate that participants will complete 8-10 surveys, which will take approximately 5-10 minutes to complete. The time to complete the surveys may vary since certain surveys will only be administered at certain time points. These surveys will be administered via tablet devices using CHES web-based platform.

Our proposed plan will investigate preliminary evidence of the efficacy of systematic monitoring of patient-reported symptomatic AEs in CML practice, in terms of self- reported adherence and pill count, HRQoL (including fatigue), and clinical response to therapy. Most importantly, this proposed study will demonstrate the ability of this

network to work together on a common project in order to best inform the development of a large international RCT.

Primary Outcome Measures

Adherence to therapy will be evaluated in two ways. These two measures are based on previously published recommendations²³, and on empirical evidence in CML indicating that pill count is associated with clinical response to TKI therapy¹¹.

Pill Count Adherence to therapy (PCA): Pill count will be based on data from the pharmacy database and computed, for each patient and scheduled treatment period, as the following proportion: (number of pills delivered at T_j – number of pills returned at T_{j+1}) $\times 100$, divided by number of pills delivered at T_j ²⁴. We will assess pill count from baseline to six months, averaged for each patient over the number of pill-count assessments. This data will be obtained from specialty oncology pharmacies in the treating clinics of the participating sites. We do not anticipate the need to obtain pill count data from entities other than the participating sites; however, should this need arise, we will obtain HIPAA authorization from these entities prior to any data collection outside of the three participating sites.

Self-reported adherence to therapy: The Adherence to Refills and Medications Scale (ARMS) will be used to evaluate self-reported adherence²⁵. ARMS will be assessed via CHES -10 at 3 and 6 months, with reassurance that treating physicians will not have access to results.

Secondary Outcome measures

Health Related Quality of life (HRQoL): The Functional Assessment of Cancer Therapy-General (FACT-G) (version 4)²⁶ will assess HRQoL. The FACT-G has four subscales: physical well-being, social / family well-being, emotional well-being, and functional well-being, with higher scores indicating better outcomes. Score range is 0-108). Selection of this questionnaire is based on its extensive use in clinical trials, and evidence indicating its sensitivity to improvement when using PRO in clinical practice¹⁶. This outcome will be evaluated at: baseline and at 3 and 6 months.

Fatigue: Fatigue, a component of HRQoL, has been chosen as one of the key patient outcome measure in this study, given previous data indicating this is a main concern for CML patients receiving TKIs^{6,27}. Fatigue will be evaluated with the PROMIS Fatigue SF13a²⁸. This outcome will be evaluated at: baseline and at 3 and 6 months.

Feasibility: Based on similar feasibility studies²⁹ feasibility is considered to be demonstrated if 80% of participants complete online questionnaires on more than 60% of follow-up visits (i.e., after initial visit up to six months) including the total number of visits across the six months of follow up (typically 8-10 visits). Reasons for missing PRO collection at follow-up visits will be recorded. This outcome will be evaluated at: 3 and 6 months.

Patient acceptability and satisfaction: An intervention-tailored questionnaire will be developed and administered using items adapted from available sources, with guidance provided by those that have been used successfully in similar research to assess patient acceptability and satisfaction²⁹. This outcome will be evaluated at: 3 and 6 months.

Physician acceptability and clinical management: After seeing each patient, physicians will be asked to take note (by completing a brief paper checklist) the clinical usefulness of the collected PRO information for the individual encounter. They will then be asked to summarize this information in a more structured ad hoc paper questionnaire reporting whether they found the PRO data valuable towards accuracy of AEs documentation, clinical decisions, or discussions with patients. This outcome will be evaluated at: 3 and 6 months.

Clinical response to therapy: During the first year, both European³⁰ and US NCCN Guidelines³¹, recommend evaluation-time benchmarks (i.e., at baseline, and at 3, 6 and 12 months) for establishing treatment efficacy. On this basis, we plan to assess TKI responses at 3 and 6 months in accordance with follow-up planned for this study. Specifically, this will be examined in two ways: 1) by inspecting the proportion of patients achieving treatment milestones, as defined by international guidelines^{30,31}; 2) by examining time to achieve treatment response.

Data analysis plan

Primary analysis

Based on H0 and H1, power and Type I error ($\alpha=0.025$) as specified in the section “Sample size”, we define the intervention achieving an *optimal adherence rate* if at least 82% of patients (n=69/84) will take at least 90% of prescribed drug (Marin D, Bazeos A, Mahon FX, et al. J Clin Oncol. May 10 2010). We define adherence as *acceptable* if at least 72% of patients (n=61/84) take at least 90% of prescribed drug. Thus, we will consider 82% and 72% as thresholds defining respectively *optimal* and *acceptable* adherence rates based on the actual number of enrolled patients. Proportions of TKI responses at three and at six months and time to achieve treatment milestones will be reported. We will estimate HRQoL and fatigue outcomes trajectories over time by a repeated measure linear mixed model, assessing possible changes from baseline by an overall F-test testing the null hypothesis of no difference. Reasons for missing PRO collection at follow-up visits will be collected as well. Based on similar studies (Basch E, Iasonos A, Barz A, et al. J Clin Oncol. Dec 01 2007; 25(34):5374-5380) the intervention will be considered feasible if at least 80% of participants complete online questionnaires at more than 60% of follow-up visits (i.e., after initial visit up to six months). We will describe all outcomes regarding feasibility, patient and physician acceptability by absolute frequencies and proportions. In addition, we will use the generalized linear mixed model (GLMM) to investigate about possible determinants of single relevant aspects (items) of acceptability, both for patients and physicians. Using the same GLMM approach, we will estimate the impact of the initial TKI on the adherence rate, accounting

for the different subject-specific number of pill count assessments over time and for the within-subject correlation of measurements. Successful management of emergent adverse events caused by the initial TKI does include the option of switching to a different TKI and we will not consider this as adherence failure. That is, we will measure adherence primarily as the composite use of all TKI agents. However, we will investigate the impact of these changes on the outcomes of interest via sensitivity analyses. We will assess the potential impact of initial TKI on different outcomes including this information as a covariate in all corresponding analyses. Unless not differently specified above, all the statistical tests will be two-sided with statistical significance set as $p < 0.05$.

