- 2) Newly diagnosed chronic phase (CP)-CML patients planned to receive one of the three TKI approved as first line treatment (i.e., imatinib, dasatinib or nilotinib);
- 3) Adult patients (≥ 18 years) at the time of study entry; Children under the age of 18 will be excluded from the study. The exclusion of children is justified by the following circumstances: a) The condition is relatively rare in children, as compared to adults; b) Issues of study preclude direct applicability of hypotheses and/or interventions to both adults and children.
- 4) Written informed consent.
- 5) Written informed consent from patient’s physician as a participant.

- 5) Newly diagnosed chronic phase (CP)-CML patients who are within 4 weeks of first line TKI therapy (any of the three TKI approved in the USA and Europe, that is: imatinib, dasatinib or nilotinib).
- 6) Ability to read/converse in English (Northwestern University and Augusta University sites). Ability to read/converse in Italian (GIMEMA site).

Patient exclusion criteria will include:

- 1) Major cognitive deficits or psychiatric problems hampering a self-reported evaluation;
- 2) Having received any CML treatment prior to therapy with imatinib, dasatinib or nilotinib for more than three months.

This project will focus on CML, which affect both men and women. Therefore, there are no exclusion/inclusion criteria based on sex/gender. In addition, there are no exclusion/inclusion criteria based on race and ethnicity.

Physician inclusion criteria will include:

- 1) Provider of clinical care for patient who meets inclusion criteria for the study

Please note that physician consent is requisite for the patient to be enrolled as a participant in the study.

4.0 Sample Size:

Sample size is based on the available resources for conducting this study. We define the adherence rate (AR) as the overall proportion of pills taken out of those prescribed, from baseline to six months, averaged over the number of pill-count assessments. Based on adherence rates reported by previous works^{10,18}, we defined 72% as a minimum threshold of AR (H0). In order to detect at least 85% of AR (H1), with power of 80% and 2.5% type I error probability (one sided exact test for binomial proportions), we will need 84 patients. However, considering overall 11% of attrition rate, 94 patients are actually required.

5.0 Recruitment and Screening Methods:

Each study site will follow the same recruitment and screening methods.

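### Adherence is defined and judged on pills prescribed, but the only pill-count formula divides by pills delivered, so missed refills go uncounted and leftovers after a TKI switch have no counting rule

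*Combined protocol and SAP*

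**What the plan says.** Section 4.0 (Sample Size) defines the adherence rate as the "overall proportion of pills taken out of those prescribed, from baseline to six months, averaged over the number of pill-count assessments". The primary analysis in section 9.0 works at patient level: the intervention reaches optimal adherence "if at least 82% of patients (n=69/84) will take at least 90% of prescribed drug", and acceptable adherence at 61/84 on the same 90% criterion.

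The only calculation is under Primary Outcome Measures in section 9.0. Pill-count adherence is "computed, for each patient and scheduled treatment period", as pills delivered at one time point minus pills returned at the next, times 100, "divided by number of pills delivered at T_j". These values are then averaged for each patient over the pill-count assessments to six months.

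On changes of drug, the Data analysis plan says that managing adverse events "does include the option of switching to a different TKI and we will not consider this as adherence failure", that "we will measure adherence primarily as the composite use of all TKI agents", and that "we will investigate the impact of these changes on the outcomes of interest via sensitivity analyses". It does not say how pills are counted when a switch happens.

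**The concern.** Delivered and prescribed are different denominators. The formula has no term for elapsed days, days of supply or prescribed quantity. A patient who finishes a supply and refills late, or never collects one, returns nothing and so loses nothing, although prescribed drug was not taken. In the other direction, a patient who stops one TKI part-way through a supply on the physician's decision and returns the rest looks non-adherent unless a rule says otherwise.

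The patient-level 90% classification feeds the 69/84 and 61/84 thresholds directly. Two analysts following the plan could therefore classify the same patient differently on the primary endpoint, and nothing written in advance would settle which of them is right. The specific aims expect physicians to reduce dose or switch drug more promptly, so changes of prescription are an intended effect of the intervention.

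**Working it through.** **The plan's own rule.** Inputs from section 4.0: H0 72%, H1 85%, one-sided 2.5%, exact binomial test, 84 patients. P(X ≥ 69 | n = 84, p = 0.72) = 0.0221 and P(X ≥ 69 | n = 84, p = 0.85) = 0.815. The design reproduces; the question is only which patients count as successes.

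**Late or uncollected refills.** Assumption: one pill a day, 30-pill fills, 180 days, nothing returned. The documents give no refill interval.

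- One fill never collected. Delivered and taken are 5 × 30 = 150, prescribed is 180. Taken over prescribed is 150/180 = 83.3%. By the formula, five periods score 30/30 and the sixth is 0/0. If that period is skipped the score is 100%; if it is set to zero the score is 5/6 = 83.3% and there is no error. The plan does not say which applies.
- Five refills, each 4 days late. Fills fall on days 0, 34, 68, 102, 136 and 170. Taken by day 180 is 5 × 30 + 10 = 160, and 160/180 = 88.9%. The formula gives 100% provided the sixth supply is left out or counted once finished. If its 20 unused pills were treated as returned at day 180, the average would be (5 × 1 + 10/30)/6 = 88.9%. The plan has no rule for a supply still open at six months.
- The same patient, averaging taken over prescribed across dispensing cycles: (5 × 30/34 + 10/10)/6 = (5 × 0.882 + 1)/6 = 90.2%, which passes. The form of averaging therefore decides this case.
- Break-even as a single ratio is more than 18 uncovered days (10% of 180). Five refills 3 days late give 165/180 = 91.7% and still pass.

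**Switch within a supply.** Take a patient who took every prescribed pill, switches once after using a fraction f of a supply, and returns the rest. With k assessments and each supply scored separately, the formula gives (k − 1 + f)/k. This is below 0.90 when f < 1 − 0.1k:

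| k | patient falls below 90% if f is under |
|---|---|
| 3 | 0.70 |
| 6 | 0.40 |
| 8 | 0.20 |
| 10 | never |

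For example, with k = 6 and 10 of 30 pills used, the score is (5 + 0.333)/6 = 88.9%. If both drugs are pooled within the period, with equal pill numbers and the new supply all taken, the condition is f < 1 − 0.2k, which cannot occur at five or more assessments. The nearest frequency in the documents is that the intervention runs for six months, "typically covering 8-10 clinical encounters", but that is not tied to pill counts.

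**Trial level, illustration only.** Suppose a share u of truly non-adherent patients passes through unseen gaps. At a true 72% the observed proportion is 0.72 + 0.28u:

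- u = 0.05: p = 0.734, P(X ≥ 69) = 0.0415 (4.1%)
- u = 0.10: p = 0.748, P(X ≥ 69) = 0.0735 (7.3%)

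In the other direction, suppose a share s of adherent patients switches within a supply and one fifth of those are misclassified (eight assessments, uniform switch timing, all leftovers returned). At a true 85% the observed proportion is 0.85 × (1 − 0.2s):

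- s = 0.05: p = 0.8415, power 0.749
- s = 0.10: p = 0.833, power 0.676

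The values of u and s are assumptions; the documents give neither.

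**The case against.** The strongest reply is that the formula refers to scheduled treatment periods. If each is supplied on time and as prescribed, delivered equals prescribed and the formula gives the intended quantity. That is correct, but nothing in the plan requires such dispensing or says what to do when it fails.

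A second reply is that a refill-and-medication self-report scale is also listed as a primary measure, and that sensitivity analyses on drug changes are planned. Both are useful, but neither enters the 69/84 rule.

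A reader might infer that the plan treats a TKI switch as non-adherence. The documents do not support this: the Data analysis plan says the opposite, and only the counting rule is missing. At 8 to 10 assessments the effect on a fully adherent switcher is also small or nil. Prescribed dose reductions and holds are not addressed in that text, so they are a gap and not a contradiction.

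A reader might also infer that every late refiller is misclassified, or that the trial's error rate is inflated by a known amount. Neither follows. Modest delays leave the patient above 90%, the 4-day example depends on how averaging is done, and the two errors run in opposite directions at unknown rates.

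**Conclusion.** The mismatch is in the text and affects the primary endpoint. As written, the delivered-pill result cannot in general be read as the share of prescribed drug taken. The clearest case is the uncollected fill, which rests on the assumed 30-day supply and on the empty period being skipped. The switch problem is narrower: a stated intention without a computation, which changes a patient's classification only when enough of a supply is returned and assessments are few.

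Net size and direction cannot be determined from the documents, and the trial-level figures only show how sensitive the rule is. This is a feasibility pilot whose sample size and decision rule stand, so the definition should be fixed before analysis; the finding does not invalidate the design.

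**What to change.** Reconcile section 4.0, the pill-count definition, the primary analysis and the paragraph on switching.

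- Define each patient's adherence as one six-month ratio, and state that it replaces the average over assessments.
- Numerator: pills taken, that is, delivered minus returned minus still in hand at six months.
- Denominator: pills prescribed under the prescription in force from baseline to six months, across all TKIs. Late or uncollected supply stays in it; pills returned because the prescription changed are not counted as missed.
- State how prescribed dose reductions and holds enter the denominator. This is a counting rule only.
- Keep the delivered-pill formula as a sensitivity analysis, with a rule for periods without a delivery.

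Check on the examples: the uncollected fill gives 150/180 = 83.3%; five refills 4 days late give (180 − 0 − 20)/180 = 88.9%; the fully adherent switcher gives 180/180 = 100% for any number of assessments. The count of pills in hand is essential, because without it the late-refill case returns 180/180.

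The 84 patients and the 69/84 and 61/84 thresholds are unchanged. The cost is rewording, abstraction of prescribed daily pill number, change dates and dispensing dates, and one count of pills in hand at six months, for about 94 patients. Pharmacy counts (section 9.0) and chart review of treatment (section 6.0) are already planned, but no dated prescription record or final pill count is described, so this is a modest addition.

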Several studies have documented the problem of non-adherence to oral TKI therapies in CML, clearly documenting that symptomatic AEs are the most frequent cause of treatment non-adherence. This has major clinical implications, as empirical evidence demonstrates that full exposure to TKI treatment schedule, is necessary to maximize response to therapy. Systematic collection of Patient-Reported Outcomes (PRO) in routine practice in other cancer conditions has shown several advantages, including the enhancing of treatment tolerability and resulting adherence. A key question that remains unanswered is whether systematic collection of relevant PRO information in routine CML care will result in improved adherence to TKI therapy and associated treatment effectiveness, including improved HRQoL.

We propose to assemble a network of treatment sites across the US (Northwestern University and Augusta University) and Italy (Italian Group for Adult Hematologic Disease, “GIMEMA”), with the goal of developing and piloting a tailored monitoring intervention targeting symptomatic, patient-reported AEs in CML patients undergoing first-line TKI therapy. The tailored monitoring intervention will draw primarily from the PRO-CTCAE Item Library, with additional items drawn from the FACIT and EORTC Item libraries as necessary. In all cases, items will be selected based on two criteria: 1) a side effect observed (any grade) in >10% of patients based on clinical trial reports of monotherapy administration; and 2) available in approved and certified English and Italian versions. After identifying the full set of AEs to be monitored, we will load the patient assessment and report program into tablets for electronic administration in the busy clinic setting. We will then pilot a six-month intervention aimed to monitor and manage emerging AEs, coupled with assessment of intervention feasibility, patient acceptability and satisfaction, provider acceptability and clinical management utility, adherence to TKI therapy, and HRQoL.

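### Averaging over whatever pill counts exist lets a patient who gives up TKI near a count, with no replacement, be scored as taking at least 90% of six months' drug

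*Combined protocol and SAP*

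**What the plan says.** Section 9.0 (Primary Outcome Measures, Pill Count Adherence) computes a proportion for each scheduled treatment period: pills delivered at one visit minus pills returned at the next, divided by pills delivered. The patient's value is then a mean: "We will assess pill count from baseline to six months, averaged for each patient over the number of pill-count assessments". Section 4.0 defines the adherence rate as "the overall proportion of pills taken out of those prescribed, from baseline to six months, averaged over the number of pill-count assessments". It divides by pills prescribed rather than delivered, but averages over counts in the same way.

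The Primary analysis text in Section 9.0 turns this into a yes/no result per patient and a study-level rule. Adherence is called optimal "if at least 82% of patients (n=69/84) will take at least 90% of prescribed drug", and acceptable at 72% of patients (61/84). The thresholds are to be applied to the number actually enrolled.

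One treatment change is addressed: switching TKI is not a failure, and "we will measure adherence primarily as the composite use of all TKI agents". No rule is given for a permanent stop without replacement, for a missing final count, for a minimum number of counts, or for scoring a patient who leaves the study. Section 19.0 allows withdrawal at any time and collects only the reasons.

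**The concern.** The label says six months, but the averaging rule shortens the window to the periods that have a count. After a permanent stop nothing is delivered, so no later period exists to pull the mean down.

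This matters because of the study's own rationale. The opening summary states that "full exposure to TKI treatment schedule, is necessary to maximize response to therapy" and names symptomatic adverse events as the commonest cause of non-adherence. A patient who gives up TKI because of side effects is the clearest case of what the intervention is meant to prevent, yet can be counted as adherent. The study has a single arm and fixed thresholds, so no control group shares the error and cancels it.

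**Working it through.** **1. Reproduce the design.** Section 4.0 gives H0 72%, H1 85%, one-sided 2.5%, power 80%, exact binomial test, N = 84. The smallest r with P(X ≥ r | n = 84, p = 0.72) ≤ 0.025 is r = 69. That gives an exact error of 0.0221, and power P(X ≥ 69 | 84, 0.85) = 0.815. The 69/84 rule reproduces. For attrition, 84 × 1.11 = 93.2 and 84/0.89 = 94.4; the stated 94 agrees within rounding.

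**2. One patient who stops at a count.** Assume monthly counts (the plan gives no pill-count schedule), two counts of 95%, then a permanent stop at day 60.
- Score as written: (95 + 95)/2 = 95%, which passes the 90% cut-off.
- Share of a 180-day window covered: 60 × 0.95/180 = 32%.

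**3. One patient who stops in mid-period, leftovers counted.** Assume equal periods and a last period half taken, scored 47.5%.
- After two good counts: (95 + 95 + 47.5)/3 = 79%, which fails.
- After five good counts: (5 × 95 + 47.5)/6 = 87%, which fails.

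The fault therefore affects stops close to a count, and stops with no final count, which leave the broken period out altogether.

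**4. Study-level effect of misscored stoppers.** Assume that 72% of patients truly reach 90% over the full window, and that a fraction m of all patients are non-adherent over that window but scored as passing. The chance of reaching the rule is P(X ≥ 69 | 84, 0.72 + m). The range of 3% to 8% stoppers is an assumption.

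| Stoppers | All pass: rate, chance | Half pass: rate, chance |
|---|---|---|
| 0% | 0.72, 0.022 | 0.72, 0.022 |
| 3% | 0.75, 0.079 | 0.735, 0.043 |
| 5% | 0.77, 0.161 | 0.745, 0.065 |
| 8% | 0.80, 0.371 | 0.76, 0.1147 |

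**5. Patients who leave the study.** Assume 10 leavers among 94 enrolled, close to the plan's 11%. Of those enrolled, 82% is 0.82 × 94 = 77.08, so 78 patients are needed. For the other 84 patients:

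| Leavers scored as | Needed from the other 84 | Chance at 85% | Chance at 72% |
|---|---|---|---|
| adherent | 78 − 10 = 68 | 0.88 | 0.040 |
| excluded (rule 69/84) | 69 | 0.81 | 0.022 |
| failures | 78 | 0.024 | <0.0001 |

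Section 4.0 adds patients for attrition, which suggests that leavers fall outside the 84. The Primary analysis text uses the number enrolled, which suggests that they stay in. Neither says how they are scored.

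**The case against.** **Different denominators.** Section 4.0 divides by pills prescribed. For a patient who abandons a drug that is still prescribed, that total could keep growing, and Section 9.0 speaks of scheduled periods. This shows that the wording needs reconciling. It does not remove the fault, because both sections average over the counts that were made, and the ratio in Section 9.0 is undefined when nothing was delivered.

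**Most stops may be caught.** A reader might infer that every early stopper scores as a success. Step 3 shows otherwise: where leftovers are counted, a mid-period stop fails the 90% cut-off. This stands, and it is why the larger figures in step 4 should not be quoted alone.

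**Leavers.** A reader might also infer that everyone who leaves early adds one to the 69/84 count. The documents do not support that. Exclusion, inclusion and failure all remain possible, so for leavers the point is an unresolved conflict and not a demonstrated upward bias.

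**The 72% reference.** It comes from earlier work that the plan cites but does not describe. If that work measured adherence on treatment only, the present rule would match it, and step 4's full-window baseline would not apply as set out.

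**Persistence is a different quantity.** Leaving the study is not stopping TKI, and a physician-directed stop is not failure to take prescribed drug. This also stands. It argues against scoring all such patients as failures, but does not excuse passing a patient who gave up treatment.

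**Conclusion.** The point holds for a defined group: patients who permanently stop on their own initiative near a count, or without a final count, and get no replacement TKI. For them the stated rule can return 90% or more when the six-month figure is far lower, and the error is always upward. In this group the rule gives a wrong answer; it is more than a missing detail.

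The study-level size cannot be fixed from the documents. Under an assumed 3% to 8% of stoppers and a true full-window rate of 72%, the chance of reaching 69/84 is 7.9% to 37% if all of them pass and about 4% to 11% if half do, against 2.2%. These are illustrations, not the trial's error rate.

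A reader might say that such a patient counts as optimal. That label belongs to the study; the patient only counts toward it. For study leavers, the handling is open and large enough to decide the primary result: 0.81 against 0.024 in step 5.

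**What to change.** - Set the window at baseline to month 6 across all TKIs, and use one denominator in Sections 4.0 and 9.0.
- In the primary classification, count a patient-initiated permanent stop without another TKI as not reaching 90%.
- Record who initiated each stop. Do not count physician-directed stops automatically as non-adherence; show them separately, with a sensitivity classification.
- For patients who leave with unknown TKI use, reconcile the attrition allowance in Section 4.0 with the enrolled denominator in the Primary analysis text. Fix one primary handling in advance, and report the result both with leavers excluded and with leavers counted as failures.
- Report the proportion still on any TKI at month 6.
- State whether the 72% reference is an on-treatment or a full-window figure.

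The cost is endpoint wording and a few tabulations from pharmacy and chart data that the study already plans to collect. The adherence figure will be less favourable. If the failure handling were made primary for leavers, the loss of power in step 5 is severe, and the sample size and thresholds would have to be reconsidered.
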